4.3.1.7 Validation of statistical programming

The analyses of the primary endpoint, secondary efficacy endpoints and frequency tables of adverse events will be essential to perform double programming. The others also double programmed as applicable.

Logs of all programs used for analysis and data preparation will be checked for errors and unexpected warnings.

Any undocumented updating of study data in statistical programs instead of change in Clinical Database (DB) (or source data) is not allowed. Specifically, this refers to the cases where patients or the data are added/ changed using a statistical program rather than updating the DB. This kind of hard coding is usually proposed to correct deficiencies (missing values, wrong values, and wrong units) in the DB when these errors are detected after DB lock. No hard coding will be done.

This policy ensures integrity of clinical data, since no changes are made to the study data without appropriate documentation from the investigator sites and appropriate audit trails within the clinical trial DB.

4.3.2 Subject Disposition

The number and percentage of subjects in each disposition category (e.g., Enrolled Population, ITT Population, PPP, Safety Population, and Completed Study, or Early Withdraw: with a breakdown of the reasons for early discontinuation) will be summarized by the subjects are treated to. Analysis will be performed using Enrolled Population.

4.3.3 Demographics and Baseline Characteristics

Demographics and Baseline characteristics (e.g., age, sex, weight, height, body mass index, disease history and prior therapies) will be summarized under group “P1101”. Analysis will be performed using ITT Population.

4.3.4 Efficacy Variables and Analysis

4.3.4.1 Efficacy Variable

The primary efficacy endpoint is the proportion (CHR) of subjects who achieved the phlebotomy-free complete hematologic response at both month 9 and month 12 without phlebotomies during the previous 3 months. Specifically, subjects who meet all the following criteria at months 9 and 12 will be classified as responder:

- Hematocrit $<45\%$ phlebotomy-free (absence of phlebotomy during the previous 3 months)
- Platelet count $\leq 400 \times 10^9/L$,
- WBC count $\leq 10 \times 10^9/L$.

Subjects, who fails to meet all the criteria or withdraw early for any reason, will be classified as non-responder.

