Study Design: This is a Phase 2 single arm study to investigate efficacy and safety of P1101 for adult Japanese patients with PV. Eligible patients will be treated with P1101, starting at 100 $\mu$ g (or 50 $\mu$ g in patients under another cytoreductive therapy). The dose should be gradually increased by 50 $\mu$ g every two weeks (in parallel, other cytoreductive therapy should be decreased gradually, as appropriate) until stabilization of the hematological parameters is achieved (hematocrit <45%, platelets <400 $\times 10^9/L$ and leukocytes <10 $\times 10^9/L$ ). The maximum recommended single dose is 500 $\mu$ g injected every two weeks.  At week 36 (month 9) and week 52 (month 12), the primary study endpoint, phlebotomy-free CHR, will be analyzed. After completion of the 52-week study duration, provision and administration of P1101, collection of the long-term follow up information (blood parameters, molecular and	

cytogenetic data, safety parameters and as also the optional bone marrow data) will be continued until the drug becomes commercially available for all study subjects..

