### **Study Procedures:**

For eligibility purposes, local lab data and local evaluations (incl. mutational status, bone marrow) will be accepted if properly documented in the source data.

Patient visits will be scheduled every 2 weeks: at regular visits, safety and AE data collection with

the basic lab investigations will be performed, while every three months (month 3, 6, 9 and 12) extended assessment visits will be scheduled. A safety follow-up visit will take place 28 days after the end of the last treatment visit.

Study procedures are detailed in the study flowchart (Appendix 1).

Pharmacokinetic (PK) samples will be collected once every 2 weeks at a timing prior to drug administration (at steady state), four consecutively at Week 0 (at first dose) and Week 28 (Appendix 2), at the end of treatment visit, and at the safety follow-up visit.

Assessment of safety will be determined by vital sign measurements, clinical laboratory tests, physical examinations, spleen size measurement by ultrasound, electrocardiogram (ECG) evaluation, lung X-ray, Eastern Cooperative Oncology Group (ECOG) performance status, ophthalmologic investigations, and the incidence and severity of treatment-emergent AEs (TEAEs).

At screening, month 9 and 12, central lab will be testing Hct, WBC and platelets for the purposes of primary endpoint analysis.

Also, a central lab will be in charge of the quantitative allelic burden measurement, as also will perform all further evaluations.

Local labs will be used for other measurement in the study.

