## **14 PRIOR AND CONCOMITANT THERAPY**

All medications (i.e., over-the-counter drugs and blood products) taken within 3 months (12 weeks) prior to the administration of the study drug, as well as, all concurrent therapies will be recorded in the relevant eCRF pages. All prior nondrug therapies, as well as, all surgeries will be recorded in the relevant eCRF pages. Dose, route, unit frequency of administration, indication for administration, and dates of medication will be captured. Any concomitant medications or changes thereof must be recorded at each visit. If the change influences the subjects' eligibility to continue in the trial, the Sponsor must be informed.

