### 17.4 Efficacy Endpoints Analysis

#### 17.4.1 Primary Efficacy Endpoint Analysis

This study will enroll 30 Japanese PV subjects and collect laboratory and clinical data on each subject every 3 months after baseline through 12 months. Primary endpoint analysis will be based on all the evaluable subjects. For each subject at each time point of 3 months, response will be assessed.

The primary efficacy endpoint is the phlebotomy-free complete hematologic responder rate (CHR) at month 9 and month 12.

The phlebotomy-free responder rate is defined as the proportion of patients with complete hematologic response (CHR) and with no phlebotomies during the previous 3 months.

A responder in sense of a primary endpoint is a patient who has met all of the following criteria at month 9 and month 12:

- Hematocrit <45% phlebotomy-free (absence of phlebotomy during the previous 3 months)
- Platelet count  $\leq 400 \times 10^9/L$ ,
- WBC count  $\leq 10 \times 10^9/L$ ,

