3.2 Study Visits/ Time-Points

Number of week and number of study visit will be included in label of study visits. The labels will be as follows: Screening, Baseline, Week 2 (V2), Week 4 (V3), Week 6 (V4), ..., Week 52 (EOT), Premature discontinuation (for End-of-Study visit of premature discontinued patients), FU (for Safety Follow-Up visit). Unscheduled visit will be labeled as 'UNS' and presented in chronological order (UNSV.c), v is visit no. and c is the times of unscheduled visit between Visit v to Visit v+1. Unscheduled visit is visit recorded as '※' in EDC.

Assessment visits will be labeled as follows: Week 12 (V7), Week 24 (V13), Week 36 (V19), Week 52 (EOT). Time-window is defined as +/- 3 days of a scheduled visit date. Deviation from the time-window will usually not be adjusted, unless specified otherwise.

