4.3.4.2 Secondary Variables

- Changes in HCT, WBC, PLT and Spleen Size from baseline
 - Absolute values and changes will be computed over study timepoint (Months 3, 6, 9 and 12)
- Time to first phlebotomy
 - Time to first phlebotomy is defined as the time interval from first dosing to first time when subject experiences a phlebotomy procedure. Subjects who completed the study and never had a phlebotomy procedure will be censored at the end of the study (Month 12). Subjects who discontinued from the study prior to any phlebotomy procedure will be censored at the time of discontinuation.
- Numbers of phlebotomy
 - Number of phlebotomy procedures experienced will be categorized as 0, 1, 2, 3 and >3.
- Disease response over time (DRT)
 - DRT will be derived from hematology parameters (Hematocrit <45% without phlebotomy (at least 3 months since last phlebotomy), and platelets $\leq 400 \times 10^9/L$, and WBCs $\leq 10 \times 10^9/L$). Central laboratory assessments will be used for disease response assessment at Weeks 12, 24, 36, 52. Patients, who withdraw early for any reason, will be classified as treatment failures in visits that they did not complete. Disease response based on local laboratory assessment will be analyzed as a sensitivity analysis if the data is available.

Protocol P1101 in Japanese PV (A19-201)

- Time to first peripheral blood count response

Time to first peripheral blood count response is defined as the time interval from first dosing to first time when achieving disease response (Hematocrit <45% without phlebotomy (at least 3 months since last phlebotomy), and platelets $\leq 400 \times 10^9/L$, and WBCs $\leq 10 \times 10^9/L$). Subjects who completed the study and never achieved response will be censored at the end of the treatment (Month 12). Subjects who discontinued prior to achieving a disease response will be censored at the time of discontinuation.

- Duration of peripheral blood count response maintenance:

Duration of response maintenance will be calculated as number of days starting from assessment visit when the response was achieved till date (excluding) of assessment visit when the response was lost. If more response period occurred within one patient, the longest period will be used for analysis. Number of days will be divided by 30.5 and results presented in months. Only subjects with response will have the duration.

- Change from baseline of *JAK2* allelic burden over time

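### Does a 3-month phlebotomy look-back with no length in days, applied at visits 16 weeks apart, undermine the primary endpoint?

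*SAP*

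**What the plan says.** SAP 4.3.4.1 defines the primary responder as a patient who meets the hematocrit, platelet and white-cell criteria "at both month 9 and month 12 without phlebotomies during the previous 3 months". Protocol 7.1, 15.3.1.1 and 17.4.1 and SAP 2.3.1.1 use the same 3-month look-back. The Protocol synopsis fixes the visits: "At week 36 (month 9) and week 52 (month 12), the primary study endpoint, phlebotomy-free CHR, will be analyzed". SAP 3.2 agrees: "Assessment visits will be labeled as follows: Week 12 (V7), Week 24 (V13), Week 36 (V19), Week 52 (EOT". The flowchart in Protocol Appendix 1 spaces the assessment visits 12 weeks apart up to month 9, so only the last interval is 16 weeks.

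The by-visit disease response in SAP 4.3.4.2 applies the same three criteria at the same visits and words the condition as "Hematocrit <45% without phlebotomy (at least 3 months since last phlebotomy". SAP 4.3.5.3 uses the same form for hematocrit target values.

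The documents convert months to shorter units only for other purposes. Protocol 14 records medication "taken within 3 months (12 weeks) prior to the administration of the study drug". For duration of response, SAP 4.3.4.2 says: "Number of days will be divided by 30.5 and results presented in months". SAP 3.10.2 also uses 30.5 days per month, for treatment duration.

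**The concern.** Two things look wrong. First, a rule that decides the primary endpoint has no length in days, so two programmers could classify the same patient differently. Second, if 3 months is elapsed time, the month-12 look-back starts at about Week 39 or 40 and the days just after Week 36 belong to neither window. Protocol 14.1 calls for phlebotomy at a hematocrit of 45% or higher, and visits are every 2 weeks. A patient could be below 45% at Week 36, be phlebotomised at Week 38, need none afterwards, and still count as phlebotomy-free at both visits.

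Compared with a rule covering all of Weeks 36 to 52, the elapsed-time rule can only add responders. About 30 patients are judged against a lower limit of 11%, so one reclassified patient at the boundary would change the result.

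**Working it through.** **The plan's own figure.** SAP 2.4 states about 85% power with 25 cases, for a true rate of 36% and a lower 95% limit above 11%. With the exact interval of SAP 4.3.5.1, 6/25 gives a lower limit of 9.36% and 7/25 gives 12.07%, so 7 responders are needed. P(X ≥ 7) for X ~ Bin(25, 0.36) is 85.2%. The figure reproduces, and the look-back does not enter it.

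**Days uncovered on the elapsed-time reading.** Week 36 is day 36 × 7 = 252 and Week 52 is day 52 × 7 = 364, an interval of 112 days. For a look-back of L days the gap is 112 − L.

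| 3 months taken as | L | Look-back from Week 52 starts | Gap (days) |
|---|---|---|---|
| 12 weeks | 84 | day 280 | 28 |
| 3 × 30.5 days | 91.5 | day 272.5 | 20.5 |
| longest three calendar months | 92 | day 272 | 20 |

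With ±3 days at each visit (SAP 3.2) the interval is 106 to 118 days, so the gap runs from 106 − 92 = 14 to 118 − 84 = 34 days. Between Week 24 and Week 36 there is no gap on schedule: 84 − L is zero or negative.

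**Where the conversions disagree.** Week 38 is day 266, before the start of the look-back in every row. All elapsed-time programmers therefore treat a Week 38 phlebotomy alike. They differ only on phlebotomies about 84 to 92 days before an assessment: days 160 to 168 for Week 36 and days 272 to 280 for Week 52. Two scheduled visits sit on the edge, Week 24 (day 168) and Week 40 (day 280). Each is exactly 84 days before an assessment, so it satisfies a minimum of 84 days but not one of 91.5 or 92.

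**Which reading the text supports.** A study-month reading, with the look-back running from the month-9 visit to the month-12 visit, would leave no gap. Its support is the synopsis ("every three months (month 3, 6, 9 and 12) extended assessment visits will be scheduled") and Protocol 17.4.1 ("collect laboratory and clinical data on each subject every 3 months after baseline through 12 months"). Both schedule visits or data collection; neither defines the look-back. The sections that do define it (Protocol 7.1; SAP 2.2.1, 2.3.1.1, 4.3.4.1, 4.3.4.2, 4.3.5.3) all describe time before the assessment or since the last phlebotomy.

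**Possible effect on the result.** Assume 30 treated patients. The exact lower limit is 9.93% for 7/30 and 12.28% for 8/30, so 8 responders are needed. Let p be the both-visits rate under the written rule and q the share of those responders phlebotomised in the gap. The documents give neither for this purpose, so both are assumptions. With X ~ Bin(30, p) and, given X, the fully covered count Y ~ Bin(X, 1 − q), the chance that the written rule passes and full coverage fails is P(X ≥ 8, Y ≤ 7):

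| q | p = 0.25 | p = 0.27 | p = 0.30 | p = 0.36 |
|---|---|---|---|---|
| 1% | 1.28% | 1.31% | 1.22% | 0.74% |
| 2% | 2.56% | 2.63% | 2.46% | 1.52% |
| 5% | 6.40% | 6.67% | 6.36% | 4.10% |

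The expected number of affected patients is 30pq, from 30 × 0.25 × 0.01 = 0.075 to 30 × 0.36 × 0.05 = 0.54.

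**The case for a change.** The strongest case for a change is that this is the primary endpoint of a small open-label trial, where a day count should be settled before anyone looks at phlebotomy dates. Double programming (SAP 4.3.1.7) does not help if both programmers work from a silent text, and Weeks 24 and 40 are real scheduled visits at which 84 and 92 days give different answers. The data needed are already collected. One could define 3 months as 92 days and require the primary responder to be phlebotomy-free from the Week 36 sample to the Week 52 sample.

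The point about the day count stands as a missing detail. It is routine content for a derivation specification, and either conversion is defensible: 12 weeks matches the visit spacing up to month 9, and 30.5 days per month is the SAP's own convention.

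The requirement for full coverage does not follow. It would replace a 3-month condition at month 12 with one of about 16 weeks, which is a new and stricter primary endpoint. It would also part company with the disease response behind the slope. SAP 2.4 joins a rate and a slope in the success rule, and both now rest on the same criteria. If the longer look-back applied only to the primary responder, a patient could respond at Week 36 and Week 52 in one analysis and fail in the other. If it applied to the Week 52 disease response as well, the four time points would no longer be comparable. In a least-squares line through the planning rates of 11%, 27%, 36% and 43% (assumed form), one responder fewer of 30 at Week 52 lowers the slope by (100/30) × 4.5/45 = 0.33 points per month, from 3.50 to 3.17. Nor do the documents say that the planning rates used a 16-week look-back.

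**Conclusion.** No change to the plan follows. The arithmetic is right: on the elapsed-time reading 20 to 28 days after Week 36 are uncovered on schedule, and 14 to 34 with visit windows. That is a property of an endpoint built from two assessments, each with a 3-month look-back. A patient phlebotomised at Week 38 who then goes 12 to 13 weeks without another and meets all criteria at Week 52 has met the endpoint as written, and the plan does not promise continuous freedom from phlebotomy.

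The day count is a gap that analysts can fill sensibly. It matters only for phlebotomies about 84 to 92 days before an assessment, and the documents give no sign that these would be common enough to affect the conclusion. The route through the Week 36 to 52 gap is narrow, and its frequency is unknown and probably low. The 0.7% to 6.7% chance of a reversed result rests on assumed shares of 1% to 5%, both-visits rates of 25% to 36%, and 30 treated patients. It compares the written rule with a stricter endpoint that the plan did not choose. Phlebotomy counts are summarised (SAP 4.3.5.4) and all database data are listed (SAP 4.3.1), so a reader who wants to see phlebotomies between the two visits can do so.

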4.3.4.2 Secondary Variables

- Changes in HCT, WBC, PLT and Spleen Size from baseline
 - Absolute values and changes will be computed over study timepoint (Months 3, 6, 9 and 12)
- Time to first phlebotomy
 - Time to first phlebotomy is defined as the time interval from first dosing to first time when subject experiences a phlebotomy procedure. Subjects who completed the study and never had a phlebotomy procedure will be censored at the end of the study (Month 12). Subjects who discontinued from the study prior to any phlebotomy procedure will be censored at the time of discontinuation.
- Numbers of phlebotomy
 - Number of phlebotomy procedures experienced will be categorized as 0, 1, 2, 3 and >3.
- Disease response over time (DRT)
 - DRT will be derived from hematology parameters (Hematocrit <45% without phlebotomy (at least 3 months since last phlebotomy), and platelets $\leq 400 \times 10^9/L$, and WBCs $\leq 10 \times 10^9/L$). Central laboratory assessments will be used for disease response assessment at Weeks 12, 24, 36, 52. Patients, who withdraw early for any reason, will be classified as treatment failures in visits that they did not complete. Disease response based on local laboratory assessment will be analyzed as a sensitivity analysis if the data is available.

Protocol P1101 in Japanese PV (A19-201)

- Time to first peripheral blood count response

Time to first peripheral blood count response is defined as the time interval from first dosing to first time when achieving disease response (Hematocrit <45% without phlebotomy (at least 3 months since last phlebotomy), and platelets $\leq 400 \times 10^9/L$, and WBCs $\leq 10 \times 10^9/L$). Subjects who completed the study and never achieved response will be censored at the end of the treatment (Month 12). Subjects who discontinued prior to achieving a disease response will be censored at the time of discontinuation.

- Duration of peripheral blood count response maintenance:

Duration of response maintenance will be calculated as number of days starting from assessment visit when the response was achieved till date (excluding) of assessment visit when the response was lost. If more response period occurred within one patient, the longest period will be used for analysis. Number of days will be divided by 30.5 and results presented in months. Only subjects with response will have the duration.

- Change from baseline of *JAK2* allelic burden over time
- Spleen size measurements by sonography will be summarized by scheduled time points, as appropriate.
- Difference in CHR rate between subject with or without of prior treatment with HU
- Proportion of subjects without thrombotic or hemorrhagic events

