## **24.7 Appendix 7. Transition phase from previous HU treatment to P1101 (for all patients on active HU)**

Transition phase is the initial part of the dose finding for the patients concurrently receiving HU at the time of screening but transferred to P1101.

The following scheme will be applied:

	HU weekly dose	P1101 dose
Week 1-2	100% of the dose at baseline	50 mcg
Week 3-12 Earliest possible HU discontinuation is being encouraged	Every two weeks, decrease the HU level 250-500 mg	Every two weeks, increase the P1101 level by 50 mcg
By week 13 onwards	discontinued	Monotherapy with dose, allowing CHR

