4.3.5.2 Disease response over time

Disease response over time (DRT) will be summarized over Months 3, 6, 9 and 12 using the same display as for CHR. The slope of the linear regression model of DRT

will be presented. These efficacy variables will be further summarized by prior HU treatment status (with or without).

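### Month 3 response, time to first response and response duration can credit hydroxyurea's effect to P1101, because the SAP ignores HU still being taken or just stopped at Week 12

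*SAP*

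**What the plan says.** **HU during the first 12 weeks.** Protocol Appendix 7 states: "Transition phase is the initial part of the dose finding for the patients concurrently receiving HU". Its scheme keeps the full baseline HU dose for Weeks 1-2. For Weeks 3-12 the instruction is "Every two weeks, decrease the HU level 250-500 mg", with the remark "Earliest possible HU discontinuation is being encouraged". HU is shown as discontinued "By week 13 onwards".

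**Scoring of response.** SAP 4.3.4.2 defines disease response over time (DRT) by hematocrit, platelets, white cells and at least 3 months since the last phlebotomy. It adds: "Central laboratory assessments will be used for disease response assessment at Weeks 12, 24, 36, 52". For the time-to-event measure: "Time to first peripheral blood count response is defined as the time interval from first dosing to first time when achieving disease response". Duration starts at the assessment visit where response was achieved. None of these definitions mentions HU.

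**Slope.** SAP 4.3.5.2 summarises DRT at Months 3, 6, 9 and 12 and presents the regression slope ("The slope of the linear regression model of DRT"). Protocol 17.2 and SAP 2.4 make a positive slope part of the success rule.

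**Related rules.** SAP 4.3.5.2 adds a summary by prior HU, yes or no. Protocol 17.8 refers intercurrent events to the SAP, which has no rule for HU. Protocol 14.2 bars other cytoreductive therapy from consent to the safety follow-up visit, which contradicts Appendix 7.

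**The concern.** A patient who enters on HU can meet the count criteria at Week 12 because of HU, P1101 or both. The SAP counts that visit as a P1101 response in three places: the Month 3 rate, the Kaplan-Meier analysis of first response, and the start of response duration.

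Eligibility makes this possible. Protocol 9.1 excludes HU-refractory patients. Its need-for-treatment criterion, which includes count thresholds, applies only to patients who have had no cytoreduction. Nothing requires uncontrolled counts in a patient already on HU, so a patient controlled by HU can enrol and be scored as an early responder.

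At stake is how quickly P1101 is said to work. With no control arm, nothing else in the trial separates the two drugs at Week 12.

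**Working it through.** **1. The plan's own power figure.** With 25 cases, the smallest count whose two-sided 95% Clopper-Pearson lower limit exceeds 11% is 7 (7/25: 12.07%; 6/25: 9.36%). With a true rate of 36%, P(X ≥ 7) = 85.2%, which matches the stated figure of about 85%. It uses the Month 9 rate only, so Month 3 does not enter it.

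**2. Timing.** SAP 3.7 makes the first dose Day 1, so the Week 12 visit is Day 1 + 84 = Day 85. SAP 3.2 says "Time-window is defined as +/- 3 days of a scheduled visit date", giving Days 82-88.
- If Appendix 7 uses visit-week labels, HU may be ongoing at the Week 12 visit.
- If its Week 1 means Days 1-7, Week 12 ends on Day 84. HU may then stop the day before the nominal visit, and can still be ongoing at a visit on Days 82-84.

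On either reading the Week 12 counts can reflect HU.

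**3. Time to first response and duration.** The next central assessment after Week 12 is Week 24. One HU-held response at Week 12 brings first response forward by at least 12 × 7 = 84 days. If response continues, duration gains the same 84 days (84/30.5 = 2.8 months), out of a maximum from Week 12 to Week 52 of 40 × 7 = 280 days.

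**4. Month 3 rate.** The documents do not say how many patients enter on HU or how many of those respond. Assume k of 30 on HU, a proportion q of them in response at Week 12, and the planning rate of 11% in the others:

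Month 3 rate = [(30 − k) × 11% + k × q] / 30

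- k = 5, q = 50%: (25 × 0.11 + 2.5)/30 = 5.25/30 = 17.5%
- k = 10, q = 50%: (20 × 0.11 + 5)/30 = 7.2/30 = 24.0%

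The rise over 11% is 6.5 to 13 points. With q from 30% to 70%, the rate is 14.2-20.8% for k = 5 and 17.3-30.7% for k = 10.

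**5. Slope.** The planning rates at Months 3, 6, 9 and 12 are 11, 27, 36 and 43% (SAP 2.4). The mean month is 7.5, the deviations are −4.5, −1.5, 1.5 and 4.5, and the sum of squares is 45.

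Slope = (−4.5 × M3 − 1.5 × 27 + 1.5 × 36 + 4.5 × 43)/45 = (207 − 4.5 × M3)/45

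| Month 3 rate | Slope (points per month) |
|---|---|
| 11% | 3.50 |
| 17.5% | 2.85 |
| 24% | 2.20 |
| 46% | 0 |

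Each point added at Month 3 lowers the slope by 0.1. On Months 6, 9 and 12 alone the slope is (43 − 27)/6 = 2.7.

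**The case against.** **The endpoints are supportive, and the HU-free rate is partly planned.** The primary endpoint needs response at both Months 9 and 12, long after the scheduled HU stop. The summary by prior HU gives a stratum with no HU taper. This stands, but the split leaves the overall rate, the Kaplan-Meier curve and the slope unchanged. The with-prior-HU stratum mixes past users with patients still tapering. The split is not clearly stated for time to first response, and it does not cover the other cytoreductive drugs that the Synopsis and SAP 2.1 allow to be tapered.

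**Patients may be off HU at the visit.** On a Day 1 week count, a compliant patient stops by Day 84. This stands as a limit: one cannot infer that patients are on HU at Week 12. It leaves the effect of HU taken up to the day before.

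**The size is uncertain.** The values of k and q are assumed. The 3-month phlebotomy condition limits how many can respond at Week 12. The 11% comes from PROUD-PV, which per Protocol 5.3 included patients currently on HU, so it may not be an HU-free rate. All of this stands.

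**Stronger readings that the documents do not support.**
- A reader might infer that HU helps the trial pass. A higher Month 3 rate flattens the slope, so it works against the slope condition.
- A reader might add 2.5/30 and 5/30 to 11% and get a rise of 8 to 17 points. That double-counts, because those patients are already in the 11% base.
- A reader might want on-HU patients scored as non-responders at Week 12. With 10 such patients, Month 3 becomes 2.2/30 = 7.3% and the slope (207 − 4.5 × 7.33)/45 = 3.9, which makes the success condition easier to meet. Response among patients still on HU would also be 0% by construction, and those who stopped the day before would be missed.

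**Conclusion.** The concern holds for the early secondary measures. Overall Month 3 DRT, time to first response and response duration can include HU's effect, and the bias favours P1101. With 5 to 10 of 30 patients on HU, half of them in response at Week 12 and 11% in the rest, Month 3 is 17.5-24% instead of 11%. These inputs are assumptions, and the true size cannot be derived from the documents.

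The success rule is not put at risk in P1101's favour. The slope falls from 3.5 to 2.85-2.2 points per month and stays above 0; at the later planning rates, Month 3 would have to reach 46% to bring it to 0. The primary endpoint and its stated power are unaffected, provided HU stops as scheduled.

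**What to change.** In SAP 4.3.4.2, 4.3.5.2, 4.3.5.5 and 4.3.5.6:

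- **(a)** Derive from the concomitant-medication dates a flag for HU or other cytoreductive use at the first P1101 dose, and the stop date of that drug.
- **(b)** Report Week 12 DRT, time to first response and duration separately by that flag, not only by any prior HU.
- **(c)** Add a sensitivity analysis for time to first response and duration. For patients on HU at first dose, the first countable response is the first assessment visit after the transition phase, Week 24.
- **(d)** Keep the planned slope over Months 3-12 for the success rule and show it also without Month 3. Do not rescore on-HU patients as non-responders in the slope.

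Protocol 14.2 and Appendix 7 contradict each other on cytoreductive therapy after consent and must be reconciled. The sponsor should also state whether Appendix 7's weeks are visit labels or counted from Day 1.

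Cost: SAP wording, one derived flag and a few extra tables. Protocol section 14 already collects medication doses and dates, so no new data are needed. The early response figures may look slightly less favourable.
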